Max	Maximum
Min	Minimum
min	Minute(s)
mL	Milliliter(s)
MMAE	monomethyl auristatin E
NCA	Noncompartmental Analysis
μg	Microgram(s)
PK	Pharmacokinetic(s)
SD	Standard Deviation
t _{1/2}	Apparent Terminal Elimination Half-Life
T _{last}	Time of Last Measurable Concentration
T _{max}	Time to Maximum Serum Concentration (C _{max})
V _z	Apparent Volume of Distribution During Terminal Phase

1. INTRODUCTION

This pharmacokinetic analysis plan describes the rules and conventions to be used in the presentation and analysis of PK data to be presented for Protocol [\[OBI-999-001\]](#). This document is based on protocol, [version 7.0](#), dated 21 July 2021.

This document reiterates key PK elements in the study design of Protocol OBI-999-001 and thoroughly describes the presentations and summaries of PK data as well as the noncompartmental analysis (NCA) to be included in the PK Report and summarized in the clinical study report (CSR) for this protocol. Shells and mockups are given for all PK-related tables, figures, and listings planned for inclusion in the CSR and/or PK Report. At minimum, mean PK plots as well as listings and summaries of OBI-999 concentrations and PK parameters will be included in the CSR, while all tables, figures, and listings described in this document will be included in the PK Report.

2. CLINICAL STUDY METHODS

2.1. Analysis Groups

This is a Phase I, open-label, dose-escalation (Part A) and cohort expansion (Part B) study of OBI-999, an antibody drug conjugate (ADC), targeting Globo H in patients with locally advanced or metastatic solid tumors. Part A is designed to establish the MTD and RP2D of OBI-999. Part B is intended to further characterize the safety and clinical activity profile of the RP2D dose of OBI-999 administered as monotherapy in patients with advanced solid tumors.

2.2. Dose Administration

OBI-999 were administered as a 60-minute intravenous (IV) infusion on Days 1 of each 21-day cycle for the initial 2 cycles (Cycle 1 and Cycle 2). The infusion duration for Cycles 3 and beyond may be reduced, at the Investigator's discretion, to 30 minutes if no infusion related AEs occur during the first 2 cycles. For Part A (Dose-Escalation), OBI-999 was planned to be given at doses of 0.4, 0.8, 1.2, 1.6, and 2.0 mg/kg (capping calculations at a maximum of 100 kg) using a 3+3 design to identify the MTD and RP2D. For Part B (Cohort-Expansion), OBI-999 will be given at the RP2D of 1.2 mg/kg (capping administered dose to a maximum of 120 mg for 100 kg)

2.3. PK Sampling Schedule

Blood (serum) samples will be collected at the following time points: C1D1 Pre-infusion (within 1 day prior-to the infusion), post infusion samples at the end of infusion and at 0.5 (± 15 min), 2 (± 15 min), 4 (± 15 min), 8 (± 15 min), 24 (± 2 h, on Day2), 72 (± 2 h, on Day4),

168 (± 2 h, on Day8), 240 (± 2 h, on Day11) and 336 hours (± 2 h, on Day15) after the end of the infusion.

2.4. Analytical Methods

As OBI-999 is an antibody drug conjugate (ADC) and composed of a humanized monoclonal IgG1 antibody conjugated with monomethyl auristatin E (MMAE, vedotin) targeting Globo H. The concentration of OBI-999 and total antibody in the serum samples were determined using a validated electrochemiluminescence (ECL) method with assay ranges of 15 to 24000 ng/mL and 100 to 15000 ng/mL, respectively. The concentration of MMAE in the serum samples were determined using a validated LC/MS/MS method with an assay range of 2 to 4000 pg/mL.

3. PHARMACOKINETIC ANALYSIS METHODS

3.1. Analysis Population and Handling of Missing Time Points

The PK population will include all enrolled subjects who receive at least 1 dose of study drug

and have sufficient PK samples (a sample at the end of administration and at least 3 samples

during the elimination phase) to include in the PK assessments. Generally, only values above the lower limit of quantification (LLOQ) are used for the estimation of PK parameters. Unless otherwise specified below, missing sampling or concentration values should not be imputed, but left missing in the calculation of derived PK parameters. If the actual sampling time is missing, but a valid concentration value has been measured, the scheduled protocol time may be used for the calculation of derived PK parameters. Collection of serum samples outside of the protocol defined time window for the time point will not result in exclusion of the sample result from NCA. Values below the lower limit of quantification (LLOQ) will be referred to as below the quantification limit (BQL). BQL values that precede the first PK concentration above the LLOQ will be imputed as 0 for linear plots and for all calculations including NCA and summary statistics. All other BQL values will be treated as missing for all analyses.

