4. LISTING OF PROPOSED TABLES, FIGURES, AND LISTINGS

PK Table 1: Summary of Demographic and Baseline Characteristics of Subjects Included in the PK Analysis Population

Parameter	PK Analysis Population (N=X)
Sex – N (%)	
Male	
Female	
Age (years)	
Mean (SD)	
Median	
Min, Max	
Height (cm)	
Mean (SD)	
Median	
Min, Max	
Weight (kg)	
Mean (SD)	
Median	
Min, Max	
BMI (kg/m²)	
Mean (SD)	
Median	
Min, Max	
Race – N (%)	
American Indian or Alaska Native	
Asian	
Black or African American	
Native Hawaiian or other Pacific Islander	
White	
Other or Unknown	

PK Table 2: Summary Statistics for Concentrations of OBI-999 by Nominal Time

Subject ID	OBI-999 Concentration (µg/mL) by Nominal Time ¹ After Dose (h)									
	0	1.5	3	5	9	25	73	169	241	337
UXX-001	X	X	X	X	X	X	X	X	X	X
UXX-002	X	X	X	X	X	X	X	X	X	X
UXX-003	X	X	X	X	X	X	X	X	X	X
...	X	X	X	X	X	X	X	X	X	X
Statistics										
N₂	X	X	X	X	X	X	X	X	X	X
Mean	X.X	X.X	X.X	X.X	X.X	X.X	X.X	X.X	X.X	X.X
SD	X.X	X.X	X.X	X.X	X.X	X.X	X.X	X.X	X.X	X.X
GM	X.X	X.X	X.X	X.X	X.X	X.X	X.X	X.X	X.X	X.X
(Min, Max)	(x, x)	(x, x)	(x, x)	(x, x)	(x, x)	(x, x)	(x, x)	(x, x)	(x, x)	(x, x)

¹ Times are relative to time of dosing.

² Number of data points used to compute the summary statistics. For calculation of summary statistics, BQL values were imputed as 0 if they did not come after a PK sample concentration that is above the LLOQ and treated as missing otherwise.

PK Table 3: Summary Statistics for Concentrations of total antibody by Nominal Time

Subject ID	Total Antibody Concentration (µg/mL) by Nominal Time ¹ After Dose (h)									
	0	1.5	3	5	9	25	73	169	241	337
UXX-001	X	X	X	X	X	X	X	X	X	X
UXX-002	X	X	X	X	X	X	X	X	X	X
UXX-003	X	X	X	X	X	X	X	X	X	X
...	X	X	X	X	X	X	X	X	X	X
Statistics										
N₂	X	X	X	X	X	X	X	X	X	X
Mean	X.X	X.X	X.X	X.X	X.X	X.X	X.X	X.X	X.X	X.X
SD	X.X	X.X	X.X	X.X	X.X	X.X	X.X	X.X	X.X	X.X
GM	X.X	X.X	X.X	X.X	X.X	X.X	X.X	X.X	X.X	X.X
(Min, Max)	(x, x)	(x, x)	(x, x)	(x, x)	(x, x)	(x, x)	(x, x)	(x, x)	(x, x)	(x, x)

¹ Times are relative to time of dosing.

² Number of data points used to compute the summary statistics. For calculation of summary statistics, BQL values were imputed as 0 if they did not come after a PK sample concentration that is above the LLOQ and treated as missing otherwise.

PK Table 4: Summary Statistics for Concentrations of MMAE by Nominal Time

Subject ID	MMAE (ng/mL) by Nominal Time ¹ After Dose (h)									
	0	1.5	3	5	9	25	73	169	241	337
UXX-001	X	X	X	X	X	X	X	X	X	X
UXX-002	X	X	X	X	X	X	X	X	X	X

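### Dropping BQL results after the first quantifiable sample biases late mean and geometric-mean concentrations upward (minor; concentration summaries and mean plots only)

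*SAP*

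**What the plan says.** SAP Appendix III section 3.1 has a two-part rule. Early BQL results become zero: "BQL values that precede the first PK concentration above the LLOQ will be imputed as 0 for linear plots and for all calculations". For the rest: "All other BQL values will be treated as missing for all analyses". Summary statistics are named among the calculations covered.

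Footnote 2 of PK Tables 2-4 (Appendix III section 4) applies the same rule to the concentration summaries: "BQL values were imputed as 0 if they did not come after a PK sample concentration that is above the LLOQ and treated as missing" in all other cases. These tables have mean, SD, GM and min/max rows at nominal times up to 337 h. Their N row is explained as "Number of data points used to compute the summary statistics".

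Section 2.4 gives the assay limits. For OBI-999 (the ADC) and total antibody it states "assay ranges of 15 to 24000 ng/mL and 100 to 15000 ng/mL, respectively", and for MMAE a "validated LC/MS/MS method with an assay range of 2 to 4000 pg/mL".

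Section 1 sets the minimum content of the report: "mean PK plots as well as listings and summaries of OBI-999 concentrations and PK parameters will be included in the CSR".

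Appendix III has no BQL count, no LLOQ/2 or censored-data rule for summaries, and no rule for withholding a mean when many samples are BQL.

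**The concern.** Leaving late BQL results out of a terminal-slope fit is ordinary practice. Leaving them out of a mean by time point is different. A BQL result is a known low value, and dropping it removes exactly the lowest patients. The mean and GM then describe only patients still above the limit, and the mean curve flattens at the LLOQ whatever the true concentration does.

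The rule is also uneven: a BQL result counts as zero before the first quantifiable sample and as no information after it.

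At stake are the late part of the mean concentration plots and the late-time comparison between doses, both of which go to readers of the study report.

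**Working it through.** **Direction.** Every dropped value is below the LLOQ and every kept value is at or above it. Removing the dropped values can only raise the mean and the GM. This needs no assumption.

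**Size.** The plan states no figure to reproduce, so the size has to be modelled.

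Inputs from the documents:
- LLOQ: 15 ng/mL for OBI-999, 100 ng/mL for total antibody, 2 pg/mL for MMAE (Appendix III 2.4).
- OBI-999 PK (protocol Table 4-1). At 0.4 mg/kg: Cmax 5.9 µg/mL, AUC 6 µg·d/mL, CL 5.3 L/day, half-life 1.8 d, Vd 8.2 L. At 1.2 mg/kg: 20.6, 29.9, 2.8, 3.6 and 6.8.
- Times after end of infusion: Day 11 = 240 h = 10 d; Day 15 = 336 h = 14 d (Appendix III 2.3).
- Three patients at the lowest dose level (SAP 5.1.1).

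Assumptions: biexponential profile, Vd read as Vss, lognormal between-patient variation with CV 20-40% on both rate constants and about 20% on scale.

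**Typical profile.** Solve A + B = Cmax; A/α + B/β = AUC; A/α² + B/β² = AUC × Vd/CL; β = ln 2 / half-life.
- 0.4 mg/kg: A = 4.85, α = 1.48/d, B = 1.05 µg/mL, β = 0.385/d. Day 15 value = 1.05 × exp(−0.385 × 14) µg/mL ≈ 4.8 ng/mL, below the 15 ng/mL limit.
- 1.2 mg/kg: A = 18.7, α = 0.93/d, B = 1.89 µg/mL, β = 0.193/d.

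**Simulation** (300,000 patients per setting; ranges run from CV 20% to CV 40%; ng/mL):

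| Setting | BQL | Mean by the rule | True mean | Overstatement |
|---|---|---|---|---|
| OBI-999, 0.4 mg/kg, Day 11 | 31-39% | 36-63 | 28-40 | +31% to +55% |
| OBI-999, 0.4 mg/kg, Day 15 | 73-88% | 24-43 | 7-14 | about 3-fold |
| OBI-999, 1.2 mg/kg, Day 15 | 0-6% | 142-185 | 142-175 | 0 to +6% |
| Total antibody at ADC level, 1.2 mg/kg, Day 15 | 34-40% | 180-259 | 142-175 | +27% to +48% |
| Total antibody at twice ADC level, 1.2 mg/kg, Day 15 | 7-21% | 301-429 | 284-349 | +6% to +23% |

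The GM moves more. At 0.4 mg/kg on Day 15 it is 22-35 by the rule against 3-4.

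**Second route for 0.4 mg/kg, Day 15.** Putting the whole AUC in the terminal phase gives an upper bound on the typical level: 0.385 × 6 × exp(−0.385 × 14) µg/mL ≈ 10.5 ng/mL. For a lognormal with median m and log-SD s, and k = ln(LLOQ/m)/s, the mean is inflated by Φ(s−k)/Φ(−k). With m = 10.5 and s from 0.3 to 2.0 this is 1.6 to 2.25 (2.05 at s = 1.0). A single exponential from Cmax would give 26.9 ng/mL and only 1.01 to 1.6, but it implies an AUC of 15.3 against the tabulated 6. The defensible range is therefore roughly 2- to 3-fold.

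**With three patients.** On Day 15 at 0.4 mg/kg, the chance that none is quantifiable is 0.88³ ≈ 0.68 at CV 20% and 0.73³ ≈ 0.39 at CV 40%. The chance of exactly one is 0.28 and 0.43. So 82-96% of such cohorts would have 0 or 1 quantifiable values.

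**MMAE.** The typical Day 15 level at 0.4 mg/kg is 70-85 pg/mL against a limit of 2 pg/mL, so little is lost.

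**The case against.** **No documented size.** The documents give no BQL fraction or variance, and the Day 15 ratio moves with the model. This stands, so the size belongs in a range. A reader might infer from the biexponential result that a threefold error is established; it is not.

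**The worst cell is nearly empty.** A Day 15 mean at 0.4 mg/kg would usually not exist or would be one patient's value. This also stands.

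**The loss is partly disclosed.** PK Tables 2-4 print each patient's value above the statistics, with N and the rule in the footnotes. PK Listings 4-6 show the reported BQL beside the analysis value, and individual profiles are plotted. This stands in part: N does not separate BQL from uncollected samples, and nothing says that the mean plots will carry a count.

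**The endpoint is untouched.** A reader might infer that half-life, clearance, AUC or dose proportionality is biased. The documents do not support that. The secondary endpoint is PK parameters, which come from each patient's own noncompartmental analysis with slope acceptance criteria, and the power model uses AUC and Cmax (Appendix III 3.4). Nor does the bias bear on the choice of RP2D, which the SAP attributes to safety review of DLTs and cumulative toxicity (SAP 5.3).

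**Total antibody is an assumption.** Table 4-1 has no total-antibody data. Protocol 4.3.3 reports similar exposure in animals; protocol 4.3.5 reports generally greater total-antibody exposure in single-dose rats. Hence both levels in the table. The minimum report content also names only OBI-999, so the total-antibody tables are clearly promised only for the PK Report.

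**Any convention has some bias.** True: LLOQ/2 for OBI-999 is 7.5 ng/mL, above the typical Day 15 value of 4.8. LLOQ/2 therefore needs a suppression rule beside it.

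**Conclusion.** The point holds as a minor one. The rule covers the concentration summaries and mean plots, and the upward direction is certain. It applies to BQL results after a patient's first quantifiable concentration; a post-dose BQL before that is set to 0, so it would be too broad to say that every post-dose BQL is dropped.

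Under the stated assumptions the OBI-999 mean at 0.4 mg/kg is about 30-55% too high on Day 11 and roughly 2- to 3-fold too high on Day 15, the latter in a cohort with usually 0 or 1 usable values. At 1.2 mg/kg, the Part B dose, OBI-999 is little affected. Total antibody on Day 15 at that dose is about 6-48% too high, depending on whether its level is twice or equal to that of the ADC.

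**What to change.** In Appendix III section 3.1 and footnote 2 of PK Tables 2-4:
- Restrict 'missing' for BQL after the first quantifiable sample to the noncompartmental analysis and the lambda-z fit.
- For PK Tables 2-4 and the mean plots, use a prespecified LLOQ/2 for those results.
- Add a row with the number of BQL samples at each time.
- Print 'BQL' instead of mean, SD and GM where more than half the samples at that time are BQL.

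In the same simulations LLOQ/2 brings the partly censored means close to the truth: 27-41 against 28-40 ng/mL at 0.4 mg/kg on Day 11, and 136-175 against 142-175 for total antibody (at the ADC level) at 1.2 mg/kg on Day 15. Where most samples are BQL it does not. At 0.4 mg/kg on Day 15 it gives 0.88 × 7.5 + 0.12 × 24 ≈ 9.5 at CV 20% and 0.73 × 7.5 + 0.27 × 43 ≈ 17 at CV 40%, against 7 and 14. The suppression rule covers that case.

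The cost is a change of wording and minor table programming, with no new data. The downside is an imputed value at partly censored times and no mean at mostly censored ones.

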3.2. Demographic and Baseline Characteristics

Sex, race, age, weight, height, and body mass index (BMI) of subjects in the PK analysis population will be listed and summarized ([PK Table 1](#), [PK Listing 1](#)).

3.3. Dosing and Pharmacokinetic Sampling Summary

Subject dose administration times will be presented ([PK Listing 2](#)). Cases that potentially affect the analysis will be discussed. Protocol deviations related to dosing or PK sampling will be listed ([PK Listing 3](#)) and summarized in the PK Report text. Deviations to be included in the PK Report include:

- Blood specimen not collected
- Serum specimen result not obtained
- Specimen temperature excursion
- Required specimen collected out of window
- Any other deviation determined by the PK analyst to be potentially affect PK

Serum concentrations will be listed by subject ([PK Listing 4-6](#)), with nominal and actual time associated with the sample indicated (nominal time is defined as the time in h since the start time of the dose). Both laboratory reported concentration values, and modified concentration values used for analysis (for instance, imputation of 0 for a BQL value at baseline) will be included, as separate columns, in the listing. Serum drug concentrations will also be summarized ([PK Table 2-4](#)) and plotted. [PK Figure 1](#) to [PK Figure 12](#) will plot all individual subject and mean serum PK profiles, as linear and semi-logarithmic plots, respectively. Subject ID for each individual profile in these figures will be shown in a legend.

3.4. Definition and Estimation of Individual NCA PK Parameters

PK parameters will be estimated through a NCA using version 8.3 or later of Phoenix® WinNonlin®

(Pharsight Corporation, Cary, NC). Actual post-dose time will be used for the estimation of PK parameters instead of nominal time. Individual PK parameter estimates will be listed ([PK Listing 7-9](#)).

Phoenix® WinNonlin® NCA will use the following settings to compute parameters from plasma PK data:

- Linear Up Log Down calculation method
- Uniform weighting
- Intravenous dose
- Plasma Model Type

- Lambda Z Acceptance Criteria

- $R_{sq_adjusted} \geq 0.80$
- $Span \geq 2.0$ half-lives
- Includes ≥ 3 timepoints after T_{max}

T_{max} (hour): Time to reach the maximum concentration

- directly taken from the observed concentration

C_{max} ($\mu\text{g/mL}$): Maximum concentration

- directly taken from the observed concentration

C_{last} ($\mu\text{g/mL}$): Concentration at last quantifiable time point

- directly taken from the observed concentration

λ (1/h): Elimination rate constant associated with the terminal phase

- estimated terminal slope of the linear regression of log-transformed concentration vs time
- The regression analysis should contain data from at least 3 different time points in the terminal phase and as many data points as possible, always including the last quantifiable concentration but excluding the concentration at T_{max} .
- The coefficient of determination Adj_RSq^2 should be larger than or equal to 0.80. If at least one of these three conditions is not fulfilled, the terminal half-life and the parameters depending on $t_{1/2}$ will be listed but flagged as not reliably calculated. They will generally be excluded from descriptive statistics and statistical testing procedures.

$t_{1/2}$ (h): Terminal elimination half-life

$$- t_{1/2} = \frac{\log_e 2}{\lambda}$$

AUC_{last} ($\text{h}^*\mu\text{g/mL}$): Area under the concentration-time curve from time zero to time the last quantifiable time, calculated by log-linear trapezoidal rule.

AUC_{∞} ($\text{h}^*\mu\text{g/mL}$): Area under the concentration-time curve from time zero to infinite time

- The percentage of extrapolated AUC should not exceed 20% of AUC_{∞} for each individual profile. If the percentage of extrapolated AUC is more than

20%, the individual AUC_{∞} result and the parameters depending on AUC_{∞} will be listed but flagged as not reliably calculated. They will generally not be included in descriptive statistics and statistical testing procedures.

$AUMC_{\text{last}}$ ($\text{h}^2 \mu\text{g}/\text{mL}$): Area under the first moment of the concentration time curve from time zero to time the last quantifiable time, calculated by log-linear trapezoidal rule.

$AUMC_{\infty}$ ($\text{h}^2 \mu\text{g}/\text{mL}$): Area under the first moment of the concentration-time curve from time zero to infinite time

CL (mL/h): Total body clearance following iv administration

$$- CL = \frac{\text{Total Dose Administered in } \mu\text{g}}{AUC_{\infty}}$$

V_z (mL): Volume of distribution following iv administration

$$- V_z = CL/\lambda$$

V_{ss} (mL): Volume of distribution at steady-state following iv administration

$$- V_{\text{ss}} = \frac{\text{Total Dose Administered in } \mu\text{g} \times AUMC}{(AUC_{\infty})^2}$$

Dose proportionality

- To investigate the dose proportionality of AUC and C_{max} , a statistical analysis using the power model will be conducted. The power model will have the form:
- $Y = a \cdot (\text{dose})^b$, where Y is the PK parameter, and a and b are the coefficient and exponent, respectively, of the power equation.
- By taking the natural logarithm (\ln), the power model can be analyzed using linear regression and has the form:
- $\ln(Y) = \ln(a) + b \cdot \ln(\text{dose}) + \text{error} = \alpha + \beta \cdot \ln(\text{dose}) + \text{error}$,
- where α is the intercept, and β is the slope, and $\ln(\text{dose})$ is based on the dose size for each subject.
- Estimates of slope and intercept along with their 90% confidence intervals will be reported. A minimum of 3 values per dose must be available for a given parameter to estimate dose proportionality using the power model.

All calculations will use the actual post-dose times recorded on the CRF. All computed PK parameters will be listed by subject and summarized by doses group in the Escalation Phase and by disease cohort in the Expansion Phase (mean, standard deviation,

coefficient of variation, minimum, maximum, number of observations). Individual and mean (by time) concentrations versus time will be plotted for each dose on both linear and natural logarithm scales.

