#### 8.3.1.1 Management of Infusion Reactions

As stated in [Section 8.2.3](#) all patients will receive prophylaxis prior to the first dose of treatment. If no infusion reactions occur with prophylactic treatments, these may be withheld for subsequent doses at the Investigator's discretion. Prophylactic treatment as described in [Section 8.2.3](#) should be resumed for all future doses if subsequent dosing without prophylaxis is associated with infusion reactions.

In the event of an infusion reaction, the OBI-999 infusion should be interrupted and medical therapy administered according to institutional standard of care.

Patients who experience a Grade 1 or Grade 2 infusion reaction may resume the infusion of drug at a reduced infusion rate (30% to 50% slower than initial rate) on the same day following appropriate medical management, as long as this falls within the 4-hour drug administration window (see [Section 8.1](#) and [Appendix 1](#)). If the 4-hour window from product reconstitution is exceeded, new drug may be prepared to administer the remainder of the planned dose.

Patients who experience a Grade 3 infusion reaction may be retreated at the discretion of the Investigator at the next scheduled treatment. Such patients should receive additional premedication that may include an acetaminophen, an antihistamine, or a corticosteroid.

Patients should be followed for at least 4 hours and until resolution of the infusion reaction. In person or telephonic follow up the next day should also be arranged to ensure there are no recurrent symptoms. Patients should also be instructed to contact study personnel if symptoms recur at later time points.

OBI-999 should be permanently discontinued in patients who experience a life-threatening (Grade 4) infusion reaction.

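### The PK plan prints the bolus formula for Vss although OBI-999 is infused over 60 minutes (about 1% too high as printed), and it does not say which AUMC to use

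*SAP*

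**What the plan says.** The PK analysis plan (SAP Appendix III) describes dosing in section 2.2: "OBI-999 were administered as a 60-minute intravenous (IV) infusion on Days 1 of each 21-day cycle for the initial 2 cycles". Protocol 8.2.2 allows 10 minutes either side, and protocol 14.4 takes the non-compartmental parameters from Cycles 1 and 2. Appendix III section 3.3 fixes the clock: "nominal time is defined as the time in h since the start time of the dose".

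Section 3.4 then defines two first-moment areas. AUMC-last is the "Area under the first moment of the concentration time curve from time zero to time the last quantifiable time". AUMC-infinity is the "Area under the first moment of the concentration-time curve from time zero to infinite time". A few lines later comes Vss, the "Volume of distribution at steady-state following iv administration", written as total dose times AUMC over the square of AUC-infinity. The AUC term carries its infinity subscript. The AUMC term carries none, and there is no term for infusion time. The software settings in the same section say only that the dose is intravenous, without bolus or infusion and without a duration.

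Section 3.4 sets a 20% limit on the extrapolated share of AUC-infinity. It sets none for AUMC. Vss is the only volume with a column in PK Tables 5 and 6 and PK Listings 7 and 8; Vz is defined but not tabulated.

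**The concern.** Vss is clearance times mean residence time. When the clock starts with a constant-rate infusion of length T, AUMC-infinity/AUC-infinity equals the mean residence time plus the mean input time, T/2. The printed formula leaves T/2 in, so it is too high for every patient, by an amount that grows with clearance and with infusion length.

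The missing subscript is a separate gap. Two analysts could follow the same line and obtain different volumes. With AUMC-last, the numerator stops at the last quantifiable sample while the denominator runs to infinity, and the shortfall differs between dose levels because it depends on half-life.

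What is at stake is the volume reported for OBI-999 and for total antibody. PK parameters are a secondary endpoint in both parts, and SAP 8.2 keeps them in the abbreviated report.

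**Working it through.** The plan states no Vss error and no AUMC extrapolation share, so there is no figure of its own to reproduce.

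**Inputs**
- Protocol Table 4-1, OBI-999, at 0.4, 0.8, 1.2 and 1.6 mg/kg: Cmax 5.9, 11.3, 20.6, 33.7 µg/mL; AUC 6, 15.8, 29.9, 60.4 µg·d/mL; CL 5.3, 4.2, 2.8, 2.6 L/day; half-life 1.8, 3.9, 3.6, 2.0 days; Vd 8.2, 8.0, 6.8, 5.7 L.
- Infusion time T = 60 min = 1/24 day.
- Last planned sample 336 h after the end of infusion, so 337 h (14.04 days) from the start (Appendix III 2.3).
- OBI-999 lower limit of quantification 15 ng/mL (Appendix III 2.4).

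**1. What Table 4-1 calls Vd.** CL x AUC gives 31.8, 66.4, 83.7 and 157.0 mg, the doses for about 79.5, 83, 70 and 98 kg, so CL = dose/AUC is plausible. CL/λ, with λ = ln 2/half-life, gives 13.8, 23.6, 14.5 and 7.5 L. These do not match the tabulated Vd, so it is not Vz as the SAP defines it. Below it is read as Vss; that is an assumption.

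**2. Missing infusion term, with AUMC-infinity.** Correct form: Vss = dose x AUMC-infinity/AUC-infinity² - dose x T/(2 x AUC-infinity). The second term is CL x T/2, which at 60 minutes is CL/48.

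| Dose (mg/kg) | CL/48 (L) | Share of Vd |
|---|---|---|
| 0.4 | 5.3/48 = 0.110 | 1.3% |
| 0.8 | 4.2/48 = 0.088 | 1.1% |
| 1.2 | 2.8/48 = 0.058 | 0.9% |
| 1.6 | 2.6/48 = 0.054 | 1.0% |

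Over 50 to 70 minutes the range is 0.7% to 1.6%. The litre figures do not depend on the reading of Vd; the percentages do.

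**3. If AUMC-last were used.** A two-exponential profile with a 60-minute infusion was matched to the tabulated Cmax, AUC, half-life and residence time Vd/CL, with Cmax placed at the end of infusion. At 1.2 mg/kg:
- λ = ln 2/3.6 = 0.1925/day; the fitted terminal phase holds 0.333 of AUC (fast rate 0.956/day).
- AUC beyond 337 h: 29.9 x 0.333 x exp(-0.1925 x 14.04) ≈ 0.67, or 2.2% of AUC.
- AUMC beyond 337 h: 0.67 x (14.04 + 1/0.1925) ≈ 12.9.
- AUMC-infinity: 29.9 x (6.8/2.8 + 1/48) ≈ 73.2, so 17.6% of AUMC is lost.
- Printed formula with AUMC-last: 83.7 x (73.2 - 12.9)/29.9² ≈ 5.65 L against 6.80 L, or -16.9%. With AUMC-infinity it gives 6.86 L.

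The net error is a little smaller than the AUMC loss because the missing T/2 term pushes the other way.

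| Dose (mg/kg) | Vss, AUMC-last (L) | Error against Vd | AUC extrapolated |
|---|---|---|---|
| 0.4 | 8.13 | -0.9% | 0.2% |
| 0.8 | 7.00 | -12.5% | 1.3% |
| 1.2 | 5.65 | -16.9% | 2.2% |
| 1.6 | 5.55 | -2.7% | 0.5% |

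Placing Cmax 30 minutes after the infusion gives -0.9%, -12.9%, -17.1% and -2.8%. In every row the extrapolated AUC is far below 20%.

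**4. An earlier last sample.** At 0.4 mg/kg the predicted 337 h level is about 5 ng/mL, below the 15 ng/mL limit; with the last value at 241 h the error is about -7%. At 1.2 mg/kg a last value at 241 h or 169 h gives about -30% or -43%, with only 5% or 9% of AUC extrapolated.

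**The case against.** The strongest reply is that AUMC-infinity is plainly meant. The denominator is AUC-infinity squared, CL is built on AUC-infinity, and Vss is the only use Appendix III could have for AUMC-infinity. A subscript may also have been lost when the text was read from PDF, although the one on AUC survived. On that reading the whole error is about 1%. This stands, and it is why the AUMC-last figures are conditional.

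Second, the parameters come from the NCA software, and a run set up as an infusion may return a corrected Vss whatever the printed line says. The dosing section states the infusion and PK Listing 2 holds start and end times. This also stands: the documents show a wrong formula and an incomplete setting, not a wrong output.

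Three stronger readings are tempting.
- *Vss will be up to 17% or 18% low.* That needs AUMC-last, Table 4-1 Vd read as Vss, a two-exponential mean profile and a quantifiable 336 h sample. It is a model estimate at one dose level, not a bound. A one-exponential profile loses between 2.9% and 28.8% of AUMC across the dose levels. For total antibody the documents give no half-life, so nothing can be computed.
- *Long infusions push the upward error to 3% to 5%.* That takes the four-hour limit as an infusion length, but the limit runs from reconstitution to completion. Protocol 8.3.1.1 lets the infusion resume after a Grade 1 or 2 reaction "at a reduced infusion rate (30% to 50% slower than initial rate) on the same day". Applied to a whole 60-minute infusion this gives about 86 to 120 minutes, and at 120 minutes an error of 1.7% to 2.7%, before any pause.
- *A false dose effect on volume.* Under AUMC-last the shortfall does differ by dose, but the only planned dose analysis, the power model, covers AUC and Cmax.

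**Conclusion.** The formula is wrong as written, and the consequence is minor. Followed as printed with AUMC-infinity, it overstates Vss by CL x T/2: 0.05 to 0.11 L, or 0.9% to 1.3%, taking Table 4-1 clearances, a constant-rate 60-minute infusion and, for the percentages, Vd as Vss.

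The unspecified AUMC matters more only if it is taken as AUMC-last. Vss would then be low by roughly 1% to 17% across dose levels on mean profiles with a quantifiable 336 h sample, and by more with an earlier last sample. The 20% AUC rule would not reveal it. The documents do not show that AUMC-last is intended.

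Vss is a descriptive secondary PK output. No efficacy or safety conclusion, and no planned test, rests on it.

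**What to change.** In Appendix III section 3.4:
- Print Vss = CL x (AUMC-infinity/AUC-infinity - T/2), with T the patient's actual infusion duration.
- State that the software dose type is intravenous infusion with that duration.
- Flag Vss for patients whose infusion was interrupted or changed in rate, because T/2 is then only approximate. For example, 10 minutes at full rate, a 60-minute stop and 100 minutes at half rate lasts 170 minutes, so T/2 is 85 minutes. The mean input time is (1/6) x 5 + (5/6) x 120 ≈ 101 minutes. One start and one end time cannot correct for this.

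The cost is one formula, one setting and one flag. Start and end times are already in PK Listing 2, and SAP 10.8.1 shows that infusion interruptions are recorded. No new data are needed. The remaining limit is that flagged patients keep an approximate Vss.
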